AZA starting dose will be between 1.5 - 2 mg/kg daily, rounded to nearest 50 mg. MPA (Myfortic) will be started 720 mg po BID and will be decreased to 360 mg BID when the Tac-IR trough level is therapeutic (according to the current goals in the center's protocol).

Immunosuppression administered at the study site will be recorded in the medical record and on a study drug diary. Immunosuppression doses administered at home will be recorded only on the study drug diary.

Tacrolimus trough target levels in both arms will be 7 to 10 ng/dL in the first month, then 5 to 7 afterward. Higher or lower tacrolimus trough level goals will be adjusted during the study due to clinical reasons such as history of rejection or infections post transplant at the discretion of the transplant nephrologists.

CBC, BMP or renal panel (including creatinine, eGFR) Tac trough levels will be checked once a week for the first four months then once every other weeks till the end of the study.

Known medication side effects: There are known common side effects to each medication. Tacrolimus has known side effects of tremors, sleep difficulty irregardless of its therapeutic range. Other side effects such as electrolyte abnormality in hyperkalemia, hypertension, and increased creatinine (if above therapeutic range) are known side effects as well. Both azathioprine and mycophenolate mofetil/mycophenoic acid have side effect of leukopenia and anemia. Azathioprine can also have elevated liver enzymes as a rarer side effect. Mycophenolate mofetil/mycophenoic acid have a known side effect of gastrointestinal upset or diarrhea.

E Study Design

E1 Overview or Design Summary

This will be an open label pilot study in which patients will be categorized into once a day regimen (Envarsus and azathioprine) or twice a day regimen (immediate release tacrolimus and mycophenoic acid) after kidney transplantation. We will enroll 50 patients in each arm after transplantation. Patients will be seen as per our usual follow up schedule until month 12 (+/- 29 days) from the time of transplant (time from transplant: week 2-4, week 5-8, week 9-12, month 6, month 9 and month 12 all +/- 2 weeks). Completion of the trial will be within 3 years. Outcomes can be reported/published by the end of the third year.

E2 Subject Selection and Withdrawal

2.a Inclusion Criteria

- Age \geq 18 years
- kidney transplant recipient
- Thymoglobulin induction

2. b Exclusion Criteria

- Non-renal organ transplant

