- Combined organ transplant
-
- Discharge to an acute-care facility after transplant

2.a Ethical Considerations

All patients will be given actual immunosuppressive medications (not placebo) in combinations that we have used in other patients at our transplant center. The only difference is one group will have medications dosed once a day and the other group will be on medications that are dosed twice a day, as per the medication administration recommendations.

2.b Subject Recruitment Plans and Consent Process

We will enroll 50 patients in each arm at the time of transplantation. Accounting for dropout of 20% from the study, we plan to possibly need to consent 120 patients total to obtain the 100 patient total number who complete the study. Subjects that meet the study inclusion criteria and without exclusion criteria will be approached in person prior to discharge from the hospital. The consenting process will be done in person by a study team member. Patients will be given the opportunity to look over the consent form and ask questions. A copy of the signed consent form will be provided to the patient once signed. Patients will be seen as part of the study until month 12 (+/- 29 days) from the time of transplant.

2.c Randomization Method and Blinding

We will approach patients after transplantation, prior to discharge. If patients are eligible to receive either tacrolimus or Envarsus, then we will approach them for participation in the study. If the patient consents to the study, we will enroll patients until we reach 50 patients in each arm of the study. There is no randomization done. Because this is an open label study, blinding is not conducted.

2.d Risks and Benefits

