We will approach patients after transplantation. Patients will either receive tacrolimus or Envarsus based on insurance coverage. We will approach patients for the study after we have determined the form of calcineurin inhibitor they will be taking. If the patient consents to the study, we will enroll patients until we reach 50 patients in each arm of the study. If needed, the antimetabolite may be transitioned to the once or twice daily dosed medication, prior to discharge so that they may receive the medications prior to their discharge from the hospital. Because this is an open label study, blinding is not conducted.

3.d Preparation and Administration of Study Drug

Study medications may be self-administered by the patient. When not on the study site, all medications will be ordered through patient's preferred pharmacy. Suggestion will be made to utilize only subspecialty pharmacies.

3.e Subject Compliance Monitoring

We may use "Pill Reminder by Medisafe" for recipients who have I-phone or android smart device. Installing the app will take place before discharge. Records from the smart phone will be emailed from the device at the clinic visit at months 3 and 12. We understand that not all patients may have a smart device/phone, and so we plan to also use a survey – BAASIS. The BAASIS survey may be distributed at months 3 and 12. Average variability in tacrolimus levels for the follow-up period preceding each of the surveys may be calculated and compared between the two groups. Pharmacies may be contacted to assess for timing between refills to ensure that patients have taken medication as scheduled.

3.f Prior and Concomitant Therapy

Patients will receive induction therapy with either anti-thymocyte globulin or basiliximab at the time of transplantation. Depending on patient's prior medical history, they may have had prior immunosuppression and may be on immunosuppression prior to their transplant. This will not interfere with the study protocol or eligibility except if they meet exclusion criteria.

3.g Packaging

Study drugs will be packaged according to standard procedures for the medication.

3.h Blinding of Study Drug

This is an open label pilot study. The patients and study members will not be blinded to the study drug.

3.i Receiving, Storage, Dispensing and Return

Study medications may be self-administered by the patient. Study medications may be administered at the study site or ordered through patient's preferred pharmacy.

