Pharmacies will be contacted to assess for timing between refills to ensure that patients have taken medication as scheduled.

Additionally, CBC, BMP or Renal panel (including creatinine, eGFR) Tac trough levels will be checked once a week for the first four months then once every other weeks as part of standard of care labs post transplant. These will be collected as data points during the study duration.

G Statistical Plan

G1 Sample Size Determination and Power

This is a pilot study. The number of patients was chosen to see if any initial evidence can be found for further investigation.

G2 Analysis Plan & Statistical Methods

Recipient characteristics will be described using proportions for categorical variables, and means with standard deviations for continuous variables. Recipient and donor factors will be compared among the groups (one a day medication group vs twice a day medication group) using a χ^2 or Fisher test for categorical variables and analysis of variance test or Kruskal Wallis tests for continuous variables, depending on the distribution of the variable.

Allograft and recipient survival will be assessed using the Kaplan-Meier survival analysis, and P values will be calculated using the log-rank test. Multivariate analysis using the Cox model will be used to calculate the hazard ratio during the follow up period for allograft failure and recipient death.

Adherence will be divided according to the level of adherence (score) into tertiles. Logistic regression will be used to examine the association between adherence and the medications group.

H Data Handling and Record Keeping

H1 Confidentiality and Security

Subject privacy: During the study we will perform medical history and examination at each recurring visit as part of standard follow-up and usual care post-transplant. Labs will be done per standard of care, and collected at each time point until 12 months post-transplant. All information collected will be for research purposes only and data will be kept in strict confidence. No information will be given to another party without the consent of the subject. We will be assigning patients a unique study number for de-identification purposes.

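### Section E2 2.b: 120 consents with 20% dropout leave about 96 completers, not the stated 100, and 100 is used for both enrolled and completing patients

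*Combined protocol and SAP*

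**What the plan says.** Section E2, 2.b (Subject Recruitment Plans and Consent Process) opens with an enrolment target: "We will enroll 50 patients in each arm at the time of transplantation". Its next sentence gives the dropout allowance: "Accounting for dropout of 20% from the study, we plan to possibly need to consent 120 patients total to obtain the 100 patient total". The end of that sentence makes clear that the 100 are completers: "to obtain the 100 patient total number who complete the study".

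Elsewhere, 50 per arm is a count of enrolled patients. E1 (Overview or Design Summary) says "We will enroll 50 patients in each arm after transplantation". Both 2.c (Randomization Method and Blinding) and 3.c (Method for Assigning Subjects to Treatment Groups) say "we will enroll patients until we reach 50 patients in each arm of the study".

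G1 (Sample Size Determination and Power) gives no calculation. It describes a pilot and says "The number of patients was chosen to see if any initial evidence can be found for further investigation". It does not say whether the number refers to enrolled or completing patients.

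**The concern.** There are two linked problems.

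- **The inflation for dropout.** One sentence gives a dropout rate, a number to consent and a number to complete, and any two of these fix the third. The stated three do not agree. The figure of 120 looks like the target plus 20% of the target, whereas a dropout rate is ordinarily a share of those who enter.
- **What the 100 counts.** If a fifth of patients are expected to leave, 100 cannot be both the number enrolled and the number completing. The protocol uses it for both, and no rule on replacing dropouts is written.

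What is at stake is operational. The consent number and the point at which enrolment closes are instructions to study staff. Someone following 2.c and 3.c to the letter could stop at 100 enrolled, while someone following 2.b would go on to 120. No loss of power, precision or validity is argued, because the plan sets no target for any of these.

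**Working it through.** **Inputs**, from section E2, 2.b: dropout d = 0.20; number consented N = 120; number completing C = 100. From E1, 2.b (first sentence), 2.c and 3.c: 50 per arm, 100 in total, as enrolled.

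**Reproducing the plan's figure.** C × (1 + d) = 100 × 1.20 = 120. The stated number is reproduced exactly, but only by applying the rate to the completers.

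**Forward check.** N × (1 − d) = 120 × 0.80 = 96 expected completers. The shortfall is 100 − 96 = 4.

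**Number needed for 100 expected completers.** C / (1 − d) = 100 / 0.80 = 125, which is 125 − 120 = 5 more than stated. Check: 125 × 0.80 = 100.

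**The same, arm by arm.** 50 / 0.80 = 62.5, rounded up to 63 per arm; 2 × 63 = 126 in total, 6 more than stated.

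**Dropout at which 120 would be enough.** 1 − 100/120 = 20/120 = 16.7%. On expectation, 120 consents yield 100 completers only if dropout is no higher than this.

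**Chance of reaching 100.** Under the added assumption that patients drop out independently with probability 0.20, completers among 120 follow a binomial distribution with mean 96 and standard deviation √(120 × 0.20 × 0.80) = √19.2 ≈ 4.4. The probability of at least 100 completers is about 21%. With 125 consents it is about 55%.

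**Enrolled or completing.**

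| Place | What is counted | Number |
|---|---|---|
| E1 | enrolled | 50 per arm |
| 2.b, first sentence | enrolled | 50 per arm |
| 2.b, second sentence | completing | 100 in total |
| 2.c and 3.c | enrolled, and the point at which enrolment ends | 50 per arm |

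If 2.c and 3.c are read literally, so that enrolment ends at 100, then 100 × 0.80 = 80 would be expected to complete. That figure is conditional: it sets aside the provision in 2.b for 120 consents.

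**The case against.** The arithmetic itself is not in dispute. The best case on the other side concerns the second part and the weight.

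- **The sentences of 2.b can be read together.** On that reading, 100 is the completion target, 120 the recruitment ceiling, and 2.c and 3.c simply use enrol loosely. This is plausible and may be what was meant. It reduces the second part to a clarification of wording and leaves the figure of 80 as an illustration only. It does not remove the inconsistency on the page, nor does it make 96 equal 100.
- **The loss might fall between consent and enrolment.** The text does not support this: the rate is described as dropout from the study, and 2.c enrols patients once they consent. Even so, losing 20% of 120 leaves 96.
- **The 20% might be meant as 20 per 100 completers.** Then the dropout rate is 16.7%, and the sentence still needs rewording.
- **The correct number might be 126.** The quota of 50 in each arm makes 126 as natural a figure as 125. Treatment follows insurance coverage (3.c), but that does not remove the quota. Since 2.b states totals, 125 is the direct correction of its sentence. The difference is one patient and alters neither the error nor the remedy.
- **The consequence is small.** This stands. The figure of 120 is hedged as a possible need, G1 sets no power or precision target, and a shortfall of 4 is smaller than one standard deviation (about 4.4) of chance variation in the number completing.

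**Conclusion.** The concern holds, as a minor one. On the plan's own figures, 120 consents lead to about 96 completers, not 100; about 125 consents are needed for 100 (126 if rounded up by arm). This rests only on reading the 20% as a share of those consented, which is the ordinary meaning of a dropout rate; no outside figure is used. The 21% probability additionally assumes independent dropout, and the conclusion does not depend on it.

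It is also correct that 50 per arm is written as enrolled in E1, the first sentence of 2.b, 2.c and 3.c, and that the second sentence of 2.b treats the same total as completing. Alone, that would be a matter of wording.

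**What to change.** Rewrite the second sentence of 2.b in one of two ways, at the sponsor's choice:

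- 120 patients consented; with 20% dropout, about 96 expected to complete. This adds no patients.
- About 125 patients consented; with 20% dropout, about 100 expected to complete. This adds 5 consents to the stated 120, or 6 if 63 per arm is used.

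Then make E1, the first sentence of 2.b, 2.c and 3.c state whether 50 per arm counts enrolled or completing patients, so that the point at which enrolment closes is unambiguous. If it counts completers, say that enrolment continues beyond 50 per arm to cover dropout, and up to what number. Apart from the 5 or 6 extra consents under the second option, the cost is a text correction.

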Although the efficacy of LCPT has been shown for use in kidney transplant patients, there is still a need for observing medication adherence with regards to the once a day treatment. This study will look at medical adherence with regards to its outcomes in kidney transplant recipients in order to better understand how a once a day regimen of tacrolimus may be beneficial to patients. Drugs work in a dose and time dependent manner and more emphasis is being put on electronic monitoring of medication adherence (Vrijens & Heidbuchel, 2015). This study may utilize Medisafe Medication Manager to accurately track adherence of the study medication.

C Study Objectives

C1 Primary Aim

Aim 1: To determine whether an immunosuppressive maintenance regimen of Envarsus/azathioprine regimen compared to a tacrolimus/ mycophenolic acid regimen is associated with better compliance and tolerability. This may be examined by a survey to the patients at 3 and 12 months. In addition, for patients with smart phone, we may examine their adherence through “Pill Manager by Medisafe” app. This app tracks missed/taken doses.

C2 Secondary Aim

Aim 2: To determine whether an Envarsus/azathioprine regimen compared to a tacrolimus/ mycophenolic acid regimen is associated with a lower composite endpoint of biopsy proven acute rejection, graft loss, death and lost to follow up at 12 months after kidney transplantation. Biopsy will be performed if clinically indicated

C3 Rationale for the Selection of Outcome Measures

Acute Rejection:

We do not perform a protocol biopsy in our center, however, we have a low threshold to do a biopsy if there is an increased creatinine, proteinuria (urine protein/ creatinine > 1 gram), or de novo DSA with high level MFI. The decision of the biopsy will be based on

the decision of the clinician. Acute rejection can lead to failure and loss of the grafted kidney and is an important endpoint in many kidney transplant studies.

Graft Failure:

Graft failure will be defined by the return to hemodialysis, re-transplantation, or patient death. Death-censored graft failure will be defined as the return to hemodialysis or re-transplantation. Graft failure was chosen due to its importance in patient outcome.

Adherence:

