Patients will all be on an immunosuppression regimen that we have used for patients we currently manage at our center. We have used both types of regimen on our patients, depending on tolerability and if there are any side effects that patients need switching to different regimens. Each regimen has been well tolerated by other patients. The major risks are with the side effects of the medications (see “11. d iii Expectedness of side effects to medications and adverse events”). It is expected that patients will adhere to the prescribed medication regimen, though some patients may not, especially to the twice daily regimen. We will attempt to mitigate this by asking patients use the pill reminder application. Patients are counselled on the importance of medication adherence for transplantation due to risk of rejection if they are not adherent. The benefits to patients include for those on the once daily regimen, less overall pill burden. Otherwise there is no additional benefit to patients.

2.e Early Withdrawal of Subjects

In the unlikely event that a patient is removed from study for unacceptable adverse event(s), such patient will be followed until resolution or stabilization of the adverse event. Participants that wish to withdraw from the study, or meet other early withdrawal material will have an End of Study/Early Termination Visit form filed. When possible or necessary, additional information about the patient (i.e. AEs, reason for withdrawal, etc.) will be gathered upon withdrawal of the study.

2.f When and How to Withdraw Subjects

Patients will be seen until month 12 (+/- 29 days) from the time of transplant. At the end of this period, an End of Study/Early Termination Visit form will be filed. Subjects will be notified of their completion or withdrawal from the study and briefed appropriately on what final steps should be taken.

2.g Data Collection and Follow-up for Withdrawn Subjects

Once withdrawn from the study, for safety reasons, patients will be followed via their labs and regular clinic visits for 12 months post withdrawal.

E3 Study Drug

3.a Description

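### Patients removed for adverse events stop giving Aim 1 data, and no analysis set or tolerability comparison brings them back, so Aim 1 may be judged mainly among patients who tolerated their regimen

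*Combined protocol and SAP*

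**What the plan says.** - **Aim (C1).** The primary aim asks whether the once-daily regimen "is associated with better compliance and tolerability". A patient survey at months 3 and 12 is the first means named, with the phone app as a supplement.
- **Removal (E2, 2.e).** "In the unlikely event that a patient is removed from study for unacceptable adverse event(s), such patient will be followed until resolution or stabilization". The section adds that adverse events and the reason for leaving are gathered at withdrawal, but only where possible or necessary.
- **After withdrawal (E2, 2.g).** "for safety reasons, patients will be followed via their labs and regular clinic visits for 12 months post withdrawal". The survey, app records and refill checks are not mentioned.
- **Switching (E2, 2.d).** Both regimens have been used at the centre, "depending on tolerability and if there are any side effects that patients need switching to different regimens". The protocol does not say how a switch within the study is handled.
- **Recruitment (E2, Subject Recruitment Plans).** "Accounting for dropout of 20% from the study", the team may need to "consent 120 patients total to obtain the 100 patient total number who complete the study". The section on randomization and blinding says "we will enroll patients until we reach 50 patients in each arm of the study", which leaves open whether 50 means enrolled or completed.
- **Analysis (G2).** Adherence tertiles are related to regimen group by logistic regression. No analysis set, rule for withdrawn or switched patients, or tolerability comparison is given. The contents list has an entry for missing outcome data, but section G has no such text.
- **Safety data (F4 to F10).** Adverse events are evaluated at Visits 1 to 6 and graded by CTCAE. Doses are updated at the same visits.

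**The concern.** A patient taken out of the study for an unacceptable adverse event is a tolerability failure, which is what Aim 1 is meant to count. As written, that patient gives no later survey or app record, and the recruitment allowance makes up the number with someone who stayed. If the analysis then uses whoever has month 12 data, the failures drop out of the comparison.

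The loss need not be equal in the two arms. D2 and F10 10.d list different side effects for the two antimetabolites: gastrointestinal upset or diarrhea for mycophenolate, and elevated liver enzymes for azathioprine. Unequal removal could hide a real tolerability difference. It would also mean that month 12 adherence is compared between groups filtered in different ways. The study is open label and not randomized, so this would add to whatever imbalance already exists. Aim 2 has some protection because its composite counts loss to follow-up as an event. Aim 1 has no equivalent.

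**Working it through.** **1. The plan's own figure.** Inputs are 100 completers and 20% dropout, from the recruitment section of E2.
- 100 × (1 + 0.20) = 120, the stated number.
- The usual inflation is 100 / (1 − 0.20) = 125.
- At 20% dropout, 120 consented leaves 120 × 0.80 = 96. Finishing with 100 of 120 means 1 − 100/120 = 16.7% dropout.

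So the plan accepts 20 patients (120 − 100) to 24 patients (120 × 0.20) without complete month 12 data. This is dropout from all causes; the share due to intolerance is not given. The gap between 120 and 125 is a separate matter and does not drive this point.

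**2. What is lost from the tolerability comparison (assumed rates).** The documents give no removal or intolerance rates. Let a proportion r of an arm be removed for adverse events and q of those remaining report poor tolerability. Among those remaining the rate is q. Counting removals as intolerance, it is r + (1 − r)q. Take q = 10% in both arms.

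| Removed, arm 1 / arm 2 | Seen among those remaining | Counting removals | Difference not seen |
|---|---|---|---|
| 20% / 5% | 10% / 10% | 0.20 + 0.80 × 0.10 = 28% / 0.05 + 0.95 × 0.10 = 14.5% | 13.5 points |
| 10% / 5% | 10% / 10% | 0.10 + 0.90 × 0.10 = 19% / 14.5% | 4.5 points |

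With 60 consented per arm, the first row needs 12 + 3 = 15 removals for adverse events, most of the planned 20 to 24 losses. The second needs 6 + 3 = 9. The first row is therefore a demanding scenario.

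**3. The same question from the true rate (assumed rates).** If p is the true intolerance rate and s the share of intolerant patients removed, the rate among the rest is p(1 − s)/(1 − ps). For p = 10% against 20%, a true difference of 10 points:
- s = 50%: 0.05/0.95 = 5.3% against 0.10/0.90 = 11.1%, difference 5.8 points.
- s = 80%: 0.02/0.92 = 2.2% against 0.04/0.84 = 4.8%, difference 2.6 points.
- s = 100%: 0 against 0, difference 0.

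If s is near zero, almost nothing is lost.

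**4. Adherence (assumed rates).** Take 60 per arm, 10 missing in each, and 15 of 50 (30%) non-adherent in both. The observed difference is 0. If all 10 missing patients in one arm are non-adherent and none in the other, the difference is (25 − 15)/60 = 16.7 points, in either direction.

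**The case against.** The strongest reply is that the plan is silent here rather than wrong. A reader might infer that every patient who cannot tolerate the regimen is removed and that Aim 1 is analysed in completers only. The documents support neither. Section 2.e calls removal unlikely and sets no criterion for it, and updating doses at every visit fits patients staying in after a change. The figure of 100 completers is a recruitment allowance, not an analysis set.

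A reader might also take 2.d to show that removal is common. It describes past switching at the centre, gives no frequency, and goes on to say that each regimen has been well tolerated. Switching is not removal.

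Nor must 2.e and 2.g be read as contradictory: one sets how long the adverse event is followed and the other how long a withdrawn patient is followed, and both can be met.

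Tolerability information is not all lost either. Adverse events before removal are recorded, side-effect surveys are mentioned, a patient removed after month 3 may already have given that survey, and labs continue.

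All of this stands, and it limits how large the effect can be claimed to be. It does not close the gap. The adverse events are collected, but G2 plans no comparison that uses them for Aim 1. The reason for withdrawal is gathered only conditionally, and nothing provides for survey, app or refill data after removal.

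**Conclusion.** The point holds as a risk that the plan leaves open, not as a demonstrated bias. Removal from the study for adverse events is foreseen, collection of adherence data after it is not provided for, recruitment aims at completers, and G2 neither fixes the Aim 1 population nor analyses tolerability. Aim 1 may therefore be judged mainly among patients who tolerated their regimen.

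The size cannot be derived from the documents. Under the assumed removal rates, 4.5 to 13.5 points of tolerability difference go unseen. That requires removals to differ by arm and the events behind them to be left out of the tolerability assessment, which the plan does not say will happen. If removals prove as rare as 2.e expects, the distortion is small. Confidence is moderate. For a pilot seeking initial evidence, this is an inexpensive improvement worth making.

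**What to change.** 1. **E2, 2.e to 2.g.** Record the stopping or switching of a study drug for an adverse event as a regimen change that does not end study data collection. Unless consent is withdrawn, the patient stays in the regimen group held at discharge and gives the month 3 and 12 surveys and outcomes at the usual clinic visits. State in one place how the follow-up in 2.e and 2.g fits together. Who stops or switches remains the clinician's decision.
2. **G2, analysis set.** Define the Aim 1 set as all enrolled patients, grouped by regimen at discharge.
3. **G2, tolerability.** Compare between groups the proportion who, by month 12, had a study drug stopped or switched, or were removed from the study, for an adverse event. Code the planned mycophenolate step-down and insurance-driven switches separately, so that they do not count as intolerance.

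**Cost.** Protocol wording, one reason-for-change code on the medication record already updated at each visit, and one table. No new visits are needed: 2.g already follows withdrawn patients at regular clinic visits for 12 months, which always reaches month 12 after transplant. The downside is that some month 12 surveys will come from patients no longer on their starting regimen, which slightly dilutes the adherence contrast.
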